**Exclusion Criteria:**

1. Subject does not have a recorded IgM level recorded within 3 months prior to ibrutinib initiation.
2. Subject meeting definition of disease progression while on ibrutinib. Subjects with IgM levels < 0.7gdL are given special consideration. Please see inclusion criteria for 2b.
3. Subjects in cohort B experiencing ongoing non hematologic toxicities attributable to ibrutinib > Grade 1 will be excluded from study entry.
4. Major surgery or a wound that has not fully healed within 4 weeks of enrollment.
5. Evidence of disease transformation at time of enrollment.
6. Evidence of or known central nervous system involvement.
7. Evidence of or known amyloidosis.
8. History of stroke or intracranial hemorrhage within 6 months prior to enrollment.
9. Requires anticoagulation with warfarin or equivalent vitamin K antagonists.
10. Requires chronic treatment with strong CYP3A inhibitors. Subjects that required strong CYP3A inhibitors can be considered for enrollment after a washout period of 14 days prior to study drug administration.
11. Requires strong CYP3A inducers. Subjects that required strong CYP3A inducers but completed a course of treatment can be considered for enrollment after a washout period of 14 days prior to study drug administration.
12. Patients with history of Chronic Obstructive Pulmonary Disease or Reactive Airway disease must have pulmonary function tests. If the subject has a FEV1 ≤ 50% of predicted normal they will be excluded.
13. Clinically significant cardiovascular disease such as uncontrolled or symptomatic arrhythmias, congestive heart failure, or myocardial infarction within 6 months of Screening, or any Class 3 (moderate) or Class 4 (severe) cardiac disease as defined by the New York Heart Association Functional Classification.
14. Vaccinated with live, attenuated vaccines within 4 weeks of randomization.
15. Seropositive for human immunodeficiency virus (HIV)
16. Seropositive for hepatitis B (defined by a positive test for hepatitis B surface antigen [HBsAg]). Subjects with resolved infection (i.e., subjects who are HBsAg negative but positive for antibodies to hepatitis B core antigen [anti-HBc] and/or antibodies to hepatitis B surface antigen [anti-HBs]) must be screened using real-time polymerase chain reaction (PCR) measurement of hepatitis B virus (HBV) DNA levels. Those who are PCR positive will be excluded. EXCEPTION: Subjects

with serologic findings suggestive of HBV vaccination (anti-HBs positivity as the only serologic marker) AND a known history of prior HBV vaccination, do not need to be tested for HBV DNA by PCR.

17. Seropositive for hepatitis C (except in the setting of a sustained virologic response [SVR], defined as aviremia at least 12 weeks after completion of antiviral therapy).
18. Any life-threatening illness, medical condition, or organ system dysfunction which, in the investigator's opinion, could compromise the subject's safety, interfere with the absorption or metabolism of ibrutinib capsules, or put the study outcomes at undue risk.
19. Active malignancy not treated with curative intent within 2 years of study entry with exception of nonmelanomatous skin cancers and cervical carcinoma in situ.

#### **Treatment Phases:**

Treatment will consist of induction, continuation, and maintenance phases. Induction will be defined as the first 2 cycles of combination treatment. The consolidation phase will include treatment with daratumumab on day 1 and day 15 of each cycle starting with cycle 3 through cycle 6. Starting at cycle 7 subjects will enter the maintenance phase with monthly daratumumab infusions until Cycle 24 day 1 (two years) at which point they will complete their combination treatment with daratumumab. Cycle 25 and beyond patients will continue on ibrutinib monotherapy.

Subjects will have doctor visits on each day of treatment with daratumumab but required study visits will only occur monthly for the first year followed by every 3 cycles for the remainder of the study. On non-study visits during induction, subjects will have baseline labwork considered to be standard of care obtained at the discretion of the investigator followed by daratumumab infusions. Subjects will take three, 140mg capsules of ibrutinib orally, daily starting on the same day as infusion and continue daily through all cycles.

#### **Treatment Administration:**

Treatment will be administered on an outpatient basis.

Ibrutinib will be administered as a single dose 420mg tablet daily for a total daily dose of 420mg. Ibrutinib naïve subjects, will have a one month lead-in Cycle -1, with ibrutinib monotherapy prior to initiating combination induction. Subjects in Cohort A who experience any Grade 3 or greater toxicity must have that toxicity resolve to Grade 1 or less prior to daratumumab combination therapy. Subjects will be asked to take a single tablet of ibrutinib orally with or without food. Subjects will take the tab on a continuous daily basis with one cycle of treatment consisting of 28 days. Subjects enrolled on the ibrutinib naïve Cohort A, will take their first dose of ibrutinib before or after their daratumumab infusion. On days in which they do not receive a daratumumab infusion they will be asked to take their ibrutinib tablet at the same time each day. Subjects will continue daily dosing of ibrutinib until disease progression, toxicities, or study completion whichever comes first.

Daratumumab will be administered per the current package insert. Subjects will receive 16mg/kg weekly for 8 total doses during induction. They will then receive 16mg/kg of daratumumab on day 1 and day 15 starting on cycle 3 through cycle 6. Starting with Cycle 7 through cycle 24 subjects will receive daratumumab 16mg/kg on day 1 until disease progression, toxicities or study completion whichever comes first.

Subjects will be premedicated with 100mg of methylprednisolone intravenously (IV), 650mg of acetaminophen PO, and 25-50mg of diphenhydramine IV all given 30 minutes prior to infusions with daratumumab. Methylprednisolone dosing may be reduced to 60mg IV with subsequent doses after the first infusion if no adverse events are recorded. Subjects will be asked to take 20mg of methylprednisolone PO for two days after each infusion and this can be eliminated at the discretion of the investigator after completion of the first cycle.

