#### **7.2. Inclusion Criteria**

- 1)** Subjects must have a diagnosis of WM and meet the requirements for active therapy as defined by the 2nd International Workshop on Waldenstrom's Macroglobulinemia (see **Appendix A** for indications for therapy).
- 2)** Age  $\geq 18$  years of age
- 3)** Ibrutinib naïve or previously treated patients currently on ibrutinib with a plateau in disease response are eligible to participate.
  - a)** Ibrutinib naïve subjects may be either treatment naïve or previously treated but ibrutinib naïve to enter cohort A.
  - b)** Subjects entering cohort B must have a plateau response on ibrutinib defined as  $\geq 6$  months of ibrutinib treatment with 2 IgM measurements at least 2 months apart with  $\leq 15\%$  change from the previous measurement. Subjects with IgM level  $< 0.7$  g/dL will be eligible if their IgM level increases  $< 0.15$  g/dL over two IgM measurements as defined above.
- 4)** Subjects must have measurable disease defined by a serum IgM level  $\geq 0.5$  g/dL
- 5)** Eastern Cooperative Oncology Group performance status of 0-2
- 6)** Hematology values must be within the following limits:

- a. Absolute neutrophil count (ANC)  $\geq 1000/\text{mm}^3$  independent of growth factor support for 7 days of study entry if cytopenias are due to marrow involvement.
- b. Platelets  $\geq 50,000/\text{mm}^3$  independent of transfusion support within 7 days of study entry. TPO mimetics are not allowed to meet eligibility criteria.
- c. Hemoglobin  $\geq 8\text{g/dL}$ , independent of transfusion support within 7 days of study entry

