### **7.3. Exclusion Criteria**

- 1) Subject does not have a recorded IgM level recorded within 3 months prior to ibrutinib initiation.**
- 2) Subject meeting definition of disease progression while on ibrutinib. Subjects with IgM levels  $< 0.7\text{g/dL}$  are given special consideration. Please see inclusion criteria for 2b.**
- 3) Subjects in cohort B experiencing ongoing non hematologic toxicities attributable to ibrutinib  $>$  Grade 1 will be excluded from study entry.**
- 4) Major surgery or a wound that has not fully healed within 4 weeks of enrollment.**
- 5) Evidence of disease transformation at time of enrollment.**
- 6) Waldenstrom's complicated by amyloidosis**
- 7) Known central nervous system lymphoma.**

- 8) History of stroke or intracranial hemorrhage within 6 months prior to randomization.
- 9) Requires anticoagulation with warfarin or equivalent vitamin K antagonists (eg, phenprocoumon).
- 10) Requires chronic treatment with strong CYP3A inhibitors. Subjects that required strong CYP3A inhibitors but completed a course of treatment can be considered for enrollment after a washout period of 14 days prior to study drug administration.
- 11) Requires strong CYP3A inducers. Subjects that required strong CYP3A inducers but completed a course of treatment can be considered for enrollment after a washout period of 14 days prior to study drug administration.
- 12) Patients with history of Chronic Obstructive Pulmonary Disease or Reactive Airway disease must have PFTs with FEV1 calculated. Patients with a  $FEV1 \leq 50\%$  of predicted normal will be excluded.
- 13) Clinically significant cardiovascular disease such as uncontrolled or symptomatic arrhythmias, congestive heart failure, or myocardial infarction within 6 months of Screening, or any Class 3 (moderate) or Class 4 (severe) cardiac disease as defined by the New York Heart Association Functional Classification.
- 14) Vaccinated with live, attenuated vaccines within 4 weeks of randomization.
- 15) Seropositive for human immunodeficiency virus (HIV)

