### 9.1. Schedule of Evaluations

Table 1. Schedule of events

Study Procedure	Screening	Cycle -1 Day -28 (Cohort A only prior to daratumumab dosing)	Cycle 1				Cycle 2			
			Week 1	Week 2	Week 3	Week 4	Week 5	Week 6	Week 7	Week 8
			Day 1	Day 8	Day 15	Day 22	Day 1	Day 8	Day 15	Day 22
Daratumumab Administration k			X	X	X	X	X	X	X	X
Informed consent	X									
Demographics	X									
Medical history	X	X	X				X			
Concurrent meds	X	X	X				X			
Physical exam	X	X	X	X	X	X	X	X	X	X
Vital signs, height, weight	X	X	X	X	X	X	X	X	X	X
CBC w/differential	X	X	X	X	X	X	X	X	X	X
Serum chemistry a	X	X	X	X	X	X	X	X	X	X
SIFE+ b	X									
Immunoglobulin M		X	X				X			
Bone marrow biopsy/aspirate c	X									
HIV and Hepatitis Ab screening d	X									
EKG	X									
Pulmonary Function Testing (FEV1 calculation)	X									
Blood Type and Screen	X		X							
Research sample (aspirate) c	X									
Research sample (peripheral blood) j	X									
Adverse event evaluation		Continuously and at each treatment or study visit								
Radiologic evaluation e	X	Radiologic measurements should be performed on Day 1 Cycle 7, 13, 19, 25, 31, 37 day 1 evaluation (+15 day window after Day 1 is allowed)								
B-HCG	X f									

Study Procedure	Cycles 3-6		Cycles 7-13 Day 1	Cycles 14, 15, 17, 18, 20, 21, 23, 24 Day 1 (non- study visits)	Cycles 16, 19, 22 Day 1 (study visits)	Cycles 25, 28, 31, 34 Day 1 (study visits)	EOT Cycle 37 Day 1 visit or 28 days after coming off-study
	Day 1	Day 15					
Daratumumab Administration k	X	X	X	X	X		
Informed consent							
Demographics							
Medical history	X		X	X	X	X	X
Concurrent meds	X		X	X	X	X	X
Physical exam	X		X	X	X	X	X
Vital signs, height, weight	X	X	X	X	X	X	X
CBC w/differential	X	X	X	X	X	X	X
Serum chemistry a	X	X	X	X	X	X	X
SIFE+ b	X g		X h		X	X	
Immunoglobulin M	X	X	X	X			X
Bone marrow biopsy/aspirate c	X i						X i
HIV and Hepatitis Ab screening d	X d		X d		X d	X d	X d
EKG							
Pulmonary Function Testing (FEV1 calculation)							
Blood Type and Screen							
Research sample (aspirate) c	X i						X i
Research sample (peripheral blood) j			X i				X i
Adverse event evaluation	Continuously and at each treatment or study visit						

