### **10. Treatment Administration**

Treatment will be administered on an outpatient basis. Appropriate dose modifications for daratumumab and ibrutinib are described in Section 6.

Ibrutinib will be administered as 3, 140mg capsules daily for a total daily dose of 420mg. Subjects will be asked to take the capsules orally with or without food. Subjects will take the pills on a continuous daily basis with once cycle of treatment consisting of 28 days. Subjects will take their first dose of ibrutinib before or after their daratumumab infusion. On days in which they do not receive a daratumumab infusion, they will be asked to take their ibrutinib capsules at the same time each day. Subjects will continue daily dosing of ibrutinib until disease progression, toxicities, or study completion whichever comes first.

Daratumumab will be administered per the current package insert. Subjects will receive 16mg/kg weekly for 8 total doses. They will then receive 16mg/kg of daratumumab every other week starting on Cycle 3-6. From Cycle 7-24, subjects will receive daratumumab 16mg/kg on an every 4 week basis until disease progression, toxicities or study completion whichever comes first. Subjects will be premedicated with 100mg of methylprednisolone intravenously (IV), 650mg of

acetaminophen PO, and 25-50mg of Benadryl IV all taking 30 minutes prior to infusions with daratumumab. Methylprednisolone dosing may be reduced to 60mg IV with subsequent doses after the first infusion if no adverse events are recorded. Subjects will be asked to take 20mg of methylprednisolone PO for two days after each infusion and this can be eliminated after completion of the first cycle at the investigators discretion if no adverse events are recorded.

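### Section 12.4 gives two different recovery grades for restarting ibrutinib after the same toxicities

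*Combined protocol and SAP*

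**What the plan says.** **Restart of ibrutinib.** Section 12.4 lists the toxicities for which both drugs are held. The last paragraph before Section 12.4.1 says that ibrutinib is restarted first, once the toxicity is Grade 2 or less, and that daratumumab follows at least 7 days later if the toxicity has not recurred. Section 12.4.2, which states that it applies to the Section 12.4 toxicities, withholds ibrutinib until Grade 1 or less at the first, second and third occurrence and discontinues it at the fourth.

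**Stopping rule.** Section 22 stops the study if 5 of the first 12 subjects have a drug-related Grade 3 or greater toxicity in the first two months that leads to a study drug hold of more than 28 days or to discontinuation of either drug.

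**Start of daratumumab in Cohort A.** The synopsis (Treatment Administration) says that Cohort A patients with any Grade 3 or greater toxicity "must have that toxicity resolve to Grade 1 or less prior to daratumumab combination therapy". Sections 9.3, 10 and 12 do not repeat this.

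**First ibrutinib dose.** The synopsis says that ibrutinib-naïve patients "will have a one month lead-in Cycle -1, with ibrutinib monotherapy prior to initiating combination induction", and Table 1 has a column headed "Cycle -1 Day -28 (Cohort A only prior to daratumumab dosing". Yet the same synopsis paragraph says "Cohort A, will take their first dose of ibrutinib before or after their daratumumab infusion", the synopsis Treatment Phases text has ibrutinib taken "daily starting on the same day as infusion and continue daily through all cycles", and Section 10 says of everyone "Subjects will take their first dose of ibrutinib before or after their daratumumab infusion".

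**The concern.** The restart level is an operative safety rule, and two sites following the protocol in good faith can apply it differently. A patient whose toxicity has improved from Grade 3 to Grade 2 may be re-dosed under the general text of Section 12.4 but not under Section 12.4.2. Section 6.2.5 says that daratumumab had not been studied clinically in this disease, so the combination's tolerability is what the trial sets out to learn.

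The level also helps fix how long a hold lasts, and hold length is one of the two routes into the Section 22 stopping count. The same clinical course could count at one site and not at another. Because daratumumab waits for ibrutinib, the conflict carries over to when daratumumab resumes.

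The two synopsis points are smaller. A site dosing from the body of the protocol could overlook the Grade 1 condition for Cohort A, and the first-dose wording is an error in dosing text for which no separate harm is claimed.

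**Working it through.** The plan gives no figure on this point, so the check sets the texts side by side.

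**1. The two restart texts**

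| Text | Toxicities covered | Ibrutinib restarts at | Daratumumab |
|---|---|---|---|
| Section 12.4, last paragraph before 12.4.1 | Section 12.4 list | Grade 2 or less | At least 7 days after ibrutinib, no recurrence |
| Section 12.4.2 | Section 12.4 list, by its own opening line | Grade 1 or less (first, second and third occurrence) | Not addressed |

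The events and the drug are the same and the levels differ by one grade. A toxicity at Grade 2 meets the first text and fails the second. Neither refers to the other or says which governs.

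**2. Link to the stopping rule.** Let t2 be the days from the start of the hold to Grade 2 or less, and t1 the days to Grade 1 or less, so t1 ≥ t2. Assume that holds are counted from the day dosing stops.

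- Ibrutinib hold: counted if longer than 28 days. The two texts give different answers when t2 ≤ 28 < t1.
- Daratumumab hold, when both drugs stop on the same day: the earliest restart is t + 7, so it exceeds 28 days when t > 28 − 7 = 21. The two texts can give different answers when t2 ≤ 21 < t1.

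The second case does not arise if daratumumab continues because the toxicity is attributed to ibrutinib, which Section 12.4 allows after discussion with the study monitor.

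**3. What cannot be computed.** The documents give no distribution of t1 or t2. For scale only, if each of 12 patients had an assumed 15%, 20%, 30% or 40% chance of a counting event, the binomial chance of 5 or more would be 2.4%, 7.3%, 27.6% or 56.2%. Nothing says which rate either restart level would produce, so no difference between these figures can be assigned to the conflict.

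**4. Section 16 figure.** At 15% of 12, x = 0.15 × 12 = 1.8. The Clopper-Pearson limits are 1.57% and 46.54%, width 44.97%, matching the stated 1.6%, 46.5% and 45.0%. The restart level does not enter this calculation.

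**5. Grade 1 condition for Cohort A.** Section 9.3 moves Cohort A from lead-in to induction with no toxicity condition, and the Cycle 1 Day 1 list in Section 9.3.1 includes the infusion with none. The hematologic triggers in Section 12.4 are Grade 4 toxicity, Grade 3 thrombocytopenia with bleeding, and febrile neutropenia. Grade 3 neutropenia without fever, Grade 3 anemia and Grade 3 thrombocytopenia without bleeding are therefore not held there, although the synopsis rule covers them.

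**6. First-dose wording.** It fits neither cohort. Cohort A starts ibrutinib one 28-day cycle before any daratumumab. Cohort B is already taking it, since "Subjects entering cohort B must have a plateau response on ibrutinib defined as" at least 6 months of treatment with a stable IgM.

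**The case against.** The best defense is that Section 12.4.2 is the specific ibrutinib rule, states Grade 1 three times and so gives a workable answer, while the sentence in Section 12.4 is mainly about order: ibrutinib first, daratumumab later. This supports choosing Grade 1 as the fix. It does not remove the conflict, because the sequencing sentence states its own recovery level for the same events.

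Four stronger readings are tempting, and the documents do not support them.

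- *Cohort A might skip the lead-in.* Table 1 and Section 9.3 set it out explicitly. The sentence after the disputed one in the synopsis and Section 10 concerns time of day, so the wording may be loose guidance for infusion days. It is an editorial fault.
- *The body contradicts the synopsis on the Grade 1 condition, exposing all 12 Cohort A patients.* The synopsis rule is in force and the body is silent, which is an omission. Section 12.4 already holds most Grade 3 or greater non-hematologic toxicity, with listed exceptions, and the more serious cytopenias. What remains is mainly an uncomplicated Grade 3 cytopenia still present at Cycle 1 Day 1. The body's related Cohort B exclusion, for "Subjects in cohort B experiencing ongoing non hematologic toxicities attributable to ibrutinib" above Grade 1, does not address cytopenias either.
- *The figure of up to 19% in Section 22 measures that gap.* It is for Grade 3 or greater hematologic toxicity on ibrutinib alone, so it includes Grade 4 events that Section 12.4 already holds, and it carries no timing.
- *The primary toxicity proportion is distorted.* Section 16 bases its precision on non-hematologic Grade 3 or greater events. A residual Grade 2 toxicity follows an index event that has already been counted if it qualifies, and a cytopenia is hematologic.

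**Conclusion.** The point holds for the restart level: Section 12.4 and Section 12.4.2 set different recovery grades for the same toxicities and the same drug. The difference is one grade and applies in both cohorts to any patient who has a listed toxicity. It can change when ibrutinib and daratumumab resume and whether a hold exceeds 28 days. How often it would do so, and whether it would change a stopping decision, cannot be determined from the documents. The 21-day and 28-day thresholds rest on counting holds from the day dosing stops, which the plan does not spell out. The sample size and the stated confidence interval are unaffected.

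The Cohort A condition is a cross-reference gap and the first-dose wording is editorial. Both merit correction, but neither carries the point.

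**What to change.** In the last paragraph of Section 12.4 before 12.4.1, change the restart level to Grade 1 or less, to match Section 12.4.2. Grade 1 is also the level in the synopsis condition for Cohort A and in the Cohort B exclusion. The sponsor should confirm that it is the intended level.

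In the same amendment, as housekeeping:

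- Repeat in Section 9.3.1 that in Cohort A any Grade 3 or greater toxicity, including hematologic, must resolve to Grade 1 or less before the first daratumumab dose.
- In the synopsis (Treatment Phases and Treatment Administration) and Section 10, replace the first-dose wording with: Cohort A starts ibrutinib on Cycle -1 Day 1; Cohort B continues its current ibrutinib.

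The cost is wording in one amendment. No visits or tests are added, since blood count, chemistry and adverse event review are already listed for Cycle 1 Day 1. Some ibrutinib holds will be longer than the Grade 2 text allowed. Because daratumumab follows by at least 7 days, it may be delayed too, and a few more holds may exceed 28 days and count toward the stopping rule. Delays over 4 weeks also bear on continued treatment under Section 11. Some Cohort A patients may start daratumumab later, as the synopsis already requires.

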### **Evaluation of Efficacy and Safety**

Response will be assessed by the investigator, based on laboratory values, physical examinations, CT scans (or MRI if CT scan is medically contraindicated), bone marrow examinations.

All measurable disease must be documented at screening by physical examination, laboratory testing, CT scan (or MRI if CT is medically contraindicated), and bone marrow. During the study, each study visit by a physical examination and laboratory testing. Clinical disease assessments will take place at baseline, monthly for the first 12 months and then every 3 months until disease progression, death or study removal for any other reason. Additional radiographic studies will be performed every 6 months on study for patients with baseline extramedullary disease. For consistency, the same method of imaging should be performed for a subject throughout the study.

[figure not shown]
